4.1. SUBJECT POPULATION

- a) **Number of Subjects:** The total sample will include 40 intervention subjects with MCI

(NIA-AA diagnostic criteria⁴⁷) and their study partner subjects (who live with or regularly visit the intervention subjects, one partner subject per intervention subject). We expect to consent and screen approximately 200 intervention subjects with MCI, resulting in a likely screen failure rate of 160 intervention subjects.

b) **Gender and Age of Subjects:** Intervention subjects with MCI must be 60-89 years, with approximately an equal number of men and women enrolled. Study partner subjects must be 18 years or older. **Racial and Ethnic Origin:** We will proactively recruit minority subjects – focusing primarily on African American and/or Hispanic/Latino groups, as both are major minority groups affected by dementia & make up most of the minority population in the Rochester area. We plan to enroll approximately 15% African American intervention subjects (about 6 intervention subjects) and about 5% of intervention subjects who are ethnically Hispanic/Latino (about 2 intervention subjects). Resulting in a total minority make-up of approximately 20% (8 intervention subjects) in our research sample. General demographics (DOB, sex, education) of the partner subjects will function as control variables considered for NPI.

Study partner-rated NPI-Q will be used to identify intervention subjects with NPS that has worsened in the past 2 years: (1) in the past month, presence of ≥ 2 symptoms; and (2) compared to 2 years ago, having ≥ 1 pre-exist symptom of which severity rating gets worsened, or having ≥ 1 new symptom. We are interested in MCI patients with worsened NPI-Q since they are the groups with highest risk for cognitive and functional decline.¹

4.2 STUDY INTERVENTIONS

Our study is registered at ClinicalTrials.gov (registration # NCT04099524).

We follow tDCS device related information according to this panel review: ⁴⁸

tDCS will be administered using a 1x1 Low-Intensity Transcranial Electrical Stimulator (tES) device (Model 2001) manufactured by Soterix Medical.

- This device is limited, by federal law, to investigational usage and does not meet any of the 7 exemption categories listed in 21 CFR §812.2. No notification from the FDA to the study sponsor requiring application approval was sent. Therefore, this device is considered to have an approved application as an IDE but will require our Institutional Review Board to make a determination regarding whether the IDE is a significant risk or not. We believe the following information may be relevant in the IRB's risk determination:
 - Meets criteria for investigation of device without significant risk: device is not intended as an implant, does not support or sustain human life, is not used for diagnostic purposes, and does not present any potential for serious risk to the health, welfare, or safety of subjects. Please see Section 9 for further information regarding the reported risks of tDCS usage (all of which are minimal).
 - Device will be labelled in accordance with 21 CFR §812.5 – including manufacturer details, quantity of contents, a cautionary statement on device contents regarding its limitations to investigational use (as required by federal law), and bears no misleading statements
 - Records will be maintained in accordance with 21 CFR §812.140 regarding maintenance

of records, including correspondences, device receipts and usage records, records of each intervention subject's case history (including informed consent, exposure to device), reports of adverse device effects, approved protocol with documented protocol deviations.

- Reports will be made in accordance with 21 CFR §812.150 – including documenting unanticipated adverse device effects and reporting to IRB & sponsor within 10 business days; reporting of withdrawal of IRB approval within 5 business days; progress reports will be submitted at least annually, reports of any deviations from investigational plans, informed consent, final study report, as well as any other information requested by either the IRB or sponsor.
- Study sponsor, investigator, and all other study team members comply with the prohibitions outlined in 21 CFR §812.7 prohibiting promotion and other practices.

4.2.1 Device Storage & Control & Accounting: The 1x1 tES device will be stored in a locked cabinet, with all of its original contents and appropriate labelling (as in accordance with 21 CFR §812.5). Only the investigator and project coordinator will have access to this locked device. Along with the device and its components, records for when the device was received by the manufacturer, when and on whom the device was used, who administered the device to the intervention subject, as well as up-to-date staff training and procedural logs will all be maintained by the investigator and project coordinator. Furthermore, all safety precautions regarding storage and usage of device outlined in the manufacturer's manual will be followed and records for compliance with storage, handling, and maintenance will be documented.

We will provide training of the stimulation to our experienced project coordinators prior to their administration of the device on intervention subjects. The training will be provided by co-I [name] who is an expert in tDCS and [name] (an experienced tDCS coordinator working on our feasibility study). Evaluation will be conducted by investigator team before a project coordinator can independently work on it.

4.2.2 Intervention Procedures:

For all 40 intervention subjects, tDCS (LPG/C3-anode, orbitofrontal cortex/Fp2-cathode) or a sham intervention will be administered for 4 weeks (1 session per weekday for 2 weeks, and then 2 sessions per week for 2 weeks, for a total of 14 sessions).

If any sessions are missed, make-up sessions will be provided, and the length of intervention period will be extended to ensure everyone receives a total of 14 sessions. Intervention subjects can choose to have the tDCS sessions where they feel comfortable (e.g., CogT Lab or their home). The maximum window for make-up sessions is two weeks.

All intervention subjects will receive anodal tDCS stimulation or a sham intervention for 20 minutes per session, on C3 and the cathode electrode on Fp2 using 10/20 EEG system (**Figure C3B**). tDCS will be applied with a pair of 35 cm² single-use sponges soaked in approximately 4mL of saline solution on each side (~8mL per sponge) connected to the stimulator. During the 20-minute tDCS session, we will use online tDCS design (i.e., an intervention subject will simultaneously work on the visual attention-oriented task.

Active tDCS Condition: We will apply the stimulation for 20 minutes using current at 1.5mA with a ramp up and ramp down period of 30 seconds at the start and end of the session (Of note, the two 30 seconds are counted in the 20-minute session).

Sham tDCS Condition: tDCS will ramp up for 30 seconds with 1 mA current and then ramp off within 10 seconds. As 30 seconds is too short for tDCS to have any effects, this will be the sham condition. tDCS is on for 30-40 seconds because that is usually the only time individuals would experience tingling and itching – a factor we aim to equate between experimental and control conditions.

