The protocol described here uses stimulation levels that fall well within established safety limits. More than 500 research studies involving thousands of subjects have been published using tDCS (source: PubMed). A number of researchers have addressed the safety of tDCS. They have all concluded that tDCS is a painless technique for safely modulating cortical excitability. No serious or long-lasting effects have been reported. A recent meta-analysis of 209 studies found no serious adverse effects. The same meta-analysis found frequent mild adverse effects, such as itching and tingling⁴⁹. All of these effects were transient and were localized to the skin at the stimulation site. A more focused study with 131 subjects undergoing 277 tDCS sessions reported similar findings: no serious adverse effects, but frequent mild effects, including itching and tingling⁵⁰. The most common mild, localized, and transient adverse effects are, in order of decreasing frequency: itching, tingling, mild headache and burning sensation. Most people do not find these sensations to be painful. Skin redness in the area of stimulation is often reported. Itching, tingling and burning usually occur at the beginning of stimulation while the current is ramped up. These sensations are reduced by gradual current ramping (as it will be done in this study). Finally, some subjects report that these sensations are uncomfortable as some individual characteristics such as type of skin and hair might result in a higher stimulation of the skin nerve receptors. tDCS has only short lived, mild effects on brain activity. To ensure safe use of the tDCS device, the device will be carefully inspected before each use. The batteries will be removed after each use to prevent corrosion that could occur after long periods of non-use. The device will be stored in a dry location. Of note, in our pilot study of older subjects (reported in the “preliminary studies” section), there have been no adverse events.

We will provide training of the stimulation to our experienced project coordinators. The training will be provided by co-I [name], who is an expert in tDCS, and [name] (an experienced tDCS coordinator working on our feasibility study). Evaluation will be conducted by investigator team before a project coordinator can independently work on it.

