The interventionists will ask every intervention subject’s study partner subject to complete the NPI-Q weekly during the intervention period to monitor changes in NPS among the intervention subjects during the 4-week tDCS sessions. If any symptoms worsen over the intervention period and a worsening is confirmed by the study partner subject, it will be reported as an adverse event (in accordance with reporting procedures described in Section 16). The intervention will then be discontinued. Our co-I, [name], who is a geriatric psychiatrist, will be notified and provide medical assessment and further advice for medical assistance.

Device-Specific Risk Minimization:

Soterix Medical outlines the same risks and risk control features for both devices, tES Model 2001 and tDCS Model 1300A, as follows:

Irritation

- The applied current may cause minor irritation, discomfort, and/or redness at the electrode sites.
- Soterix Medical *EASYPad*™ electrodes should not be placed over previously irritated, burnt, or damaged skin.

Methods of Risk Minimization:

- **SMARTscan™**: a visual 20 bar LED display (1 to 20 from left to right) that indicates to the

operator the contact conditions of the electrodes before, during, and after stimulation. LED 1 denotes short condition and LED 2 denotes open-circuit condition. Stimulation should not begin if either LED 1 or LED 2 is lit.

- **PRE-STIM TICKLE:** a pre-stimulation feature that conditions the skin prior to full stimulation,
- **RELAX:** a feature that allows the operator to decrease the set level of current from the maximum (FULL CURRENT) value to accommodate subject feedback at any point without aborting the stimulation session.
- **TRUE CURRENT™** display is active whenever the device is on and indicates the actual value of current (in mA) being supplied from the device to the electrodes, regardless of device settings. This feature functions as a fully independent and redundant safety feature when monitored by the operator.

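### Sham ramps to 1 mA and active to 1.5 mA over the same 30 s, with no reason given, although the plan aims to equate tingling and itching between arms

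*Combined protocol and SAP*

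**What the plan says.** Section 4.2.2 (Intervention Procedures) gives both arms the same montage (C3 anode, Fp2 cathode), the same 35 cm² sponges and a 20-minute session. The active arm is stimulated "using current at 1.5mA with a ramp up and ramp down period of 30 seconds", and both ramps count within the 20 minutes. For the sham arm, "tDCS will ramp up for 30 seconds with 1 mA current and then ramp off within 10 seconds".

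The same section defends the sham on time alone: "As 30 seconds is too short for tDCS to have any effects, this will be the sham condition". It adds that the current is on for 30-40 s because tingling and itching are usually felt only then, and calls them "a factor we aim to equate between experimental and control conditions".

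Section 9 (Risks, tDCS conditions) says: "Itching, tingling and burning usually occur at the beginning of stimulation while the current is ramped up". Its next sentence says that ramping gradually lessens these sensations.

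Section 4 requires participants and study partners to be blinded, with unblinding only once the follow-up assessment is complete. Interventionists know the allocation.

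**The concern.** The plan sets itself a matching aim and then matches only one of the two settings that define the onset stimulus. Ramp-up time is 30 s in both arms, but peak current is not the same. No section explains the choice of 1 mA.

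What is at stake is blinding. If the sham feels weaker at onset, some participants might form a view of their arm, and the stimulus recurs over 14 sessions. Self-reports such as the GDS, STAI and MFI would be the first place for such a view to show. Partner-rated NPS, the secondary endpoint behind H2a, could be touched only if the participant conveyed that view to the partner. Table 1 lists no arm-guess question and no per-session sensation form, so the data would not show whether the mismatch was harmless.

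**Working it through.** **Inputs.** All come from Section 4.2.2: active peak 1.5 mA with 30 s up and 30 s down inside a 1200 s session; sham peak 1.0 mA with 30 s up and off in at most 10 s; sponge area 35 cm² in both arms. **Assumption:** ramps are linear from and to zero.

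**The plan's own figure.** Sham on-time = 30 + up to 10 = up to 40 s, which agrees with the stated 30-40 s.

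**Onset stimulus.**
- Ramp rate = peak / ramp time. Active 1.5/30 = 0.050 mA/s; sham 1.0/30 = 0.033 mA/s. Ratio 1.0/1.5 = 0.67, so the sham is one third gentler.
- Active passes the sham peak at 1.0/0.050 = 20 s and rises for another 10 s.
- Peak density = peak / area. Active 1.5/35 = 0.043 mA/cm²; sham 1.0/35 = 0.029 mA/cm².

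**Charge per session** (mA × s = mC; a linear ramp contributes half of peak × time).
- Active: 0.5 × 30 × 1.5 + 1140 × 1.5 + 0.5 × 30 × 1.5 = 22.5 + 1710 + 22.5 = 1755 mC.
- Sham now, with a 10 s ramp-off: 0.5 × 30 × 1.0 + 0.5 × 10 × 1.0 = 15 + 5 = 20 mC; 20/1755 = 1.1%.
- Sham at 1.5 mA, 30 s up and 10 s off: 22.5 + 0.5 × 10 × 1.5 = 22.5 + 7.5 = 30 mC; 30/1755 = 1.7%. On-time 30 + 10 = 40 s.

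**Ramp-off rate.** Now at least 1.0/10 = 0.10 mA/s (a minimum, since the text sets only an upper limit on the time). After the change 1.5/10 = 0.15 mA/s. The active ramp-down is 1.5/30 = 0.05 mA/s.

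**Sensitivity to wording.** The sham sentence could be read as 1 mA held for the full 30 s. Charge would then be 30 + 5 = 35 mC (35/1755 = 2.0%), and sham current would exceed active current until 20 s. The 0.5 mA gap in peak remains on either reading. The one-third difference in ramp rate depends on the linear reading, which is the more natural one.

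**Consistency with the plan's reasoning.** Section 9 places sensation in the ramp-up and says a gentler ramp lessens it. On the linear reading the sham has the gentler ramp in that period. Section 4.2.2 attributes sham inertness to duration, and duration does not change if the peak is raised to 1.5 mA with a 10 s ramp-off.

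**The case against.** The strongest reply is that nothing shows the difference can be felt. Each participant receives one setting and has no direct comparator. The documents give no relation between current and sensation over 1 to 1.5 mA. This stands, and it means the effect on blinding may be nil.

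Second, the plan may mean to equate sensation through on-time and never promises equal amplitude. That is a fair account of the method, but the factor named is the sensation itself, and Section 9 ties it to how the current is ramped.

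Third, the device text in Section 9 might be used to argue that the plan itself treats current level as driving sensation: "The applied current may cause minor irritation, discomfort, and/or redness at the electrode sites", and RELAX is "a feature that allows the operator to decrease the set level of current from the maximum (FULL CURRENT) value to accommodate subject feedback". These are the manufacturer's general descriptions and give no dose-response, so they add little. They do matter in another way. RELAX, and PRE-STIM TICKLE, "a pre-stimulation feature that conditions the skin prior to full stimulation", could change early sensation, and the plan does not say whether they are used or used alike in both arms.

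Fourth, the self-reports most exposed are listed in Section 4 under other measures, and this is a 40-person Stage 0 study. That limits the weight of the point but does not explain the 1 mA.

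The pilot in Section 2 does not settle the matter. It reports no adverse effects in 14 people, but no comparison of sensation by arm and no blinding result.

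**Conclusion.** The mismatch is real and unexplained: sham peak current is 67% of active over the same 30 s and, if the ramps are linear, the sham ramp is one third gentler. It departs from the plan's stated aim and brings no benefit that the plan claims. It is an avoidable risk to participant blinding and, at one remove, to partner-rated NPS. The size of any effect on blinding or on NPI scores cannot be derived from the documents and could be zero.

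A reader might infer that blinding fails in this trial, or that the H2a comparison is biased. The documents do not support either, since they hold no evidence that participants can perceive the difference. A reader might also extend the point to the primary endpoints. Those are resting-state and task fMRI measures, and nothing in the documents links onset sensation to them.

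The point is worth acting on because the aim is the plan's own and the change is nearly free. Confidence is medium.

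**What to change.** Before enrolment, ramp the sham to 1.5 mA over 30 s exactly as in the active arm, then ramp off over 10 s. Write a ramp-off of 10 s in place of the present upper limit, because the ABORT text in Section 9 advises against ramp-downs shorter than 10 s. State that PRE-STIM TICKLE and RELAX, if used, are used in the same way in both arms. If there is a reason for keeping 1 mA, state it.

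The cost is one changed current setting, a firm ramp-off time and one sentence. Sham exposure rises by about 10 mC per session (30 − 20, linear ramps), and the ramp-off steepens to 0.15 mA/s. A 30 s ramp-down to mirror the active arm is tempting, but it would bring on-time to 30 + 30 = 60 s, outside the 30-40 s on which the plan bases its sham.

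If participants are already enrolled, leave the sham setting alone, since a change part-way would alter the control condition, and report the mismatch as a limitation.

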5. INCLUSION AND EXCLUSION CRITERIA

a) Inclusion Criteria:

1. Forty intervention subjects with MCI and comorbid NPS, which have worsened in the past 2 years (as rated by their study-partner subject's responses to the NPI-Q):
 - (1) In the past month, presence of ≥ 2 symptoms; and
 - (2) Compared to two years ago, having ≥ 1 pre-existing symptom whose severity rating has worsened, or having ≥ 1 new symptom;
2. Consensus diagnosis of “mild cognitive impairment due to Alzheimer’s disease” based on 2011 NIA-AA diagnostic criteria by the investigators based on screening information:
 - i. Memory deficits at screening: 1 standard deviation (SD) below age- and/or education- corrected population norms for the Rey Auditory Verbal Learning Test (RAVLT, Lists C&D);
 - ii. Global memory deficits at screening: Montreal Cognitive Assessment (MoCA, Version 2) total score within the range $18 \leq x \leq 26$, after educational adjustment;
 - iii. Preserved activity of daily living: ADL-PI-self total score ≤ 30 ;
 - iv. Absence of dementia.
3. Stable (same dosage, frequency, type) on memory medications for ≥ 3 months before screening;
4. Stable (same dosage, frequency, type) on any anti-depressants, antipsychotics, and/or anxiolytics for ≥ 7 days;
5. Community-dwelling: Intervention subjects live in homes or independent- and assisted-living facilities (i.e. – not nursing home residents, due to the large cognitive variability in nursing home residents);
6. Aged 60-89 years at screening;
7. English-speaking;
8. Adequate visual and hearing acuity for testing;
9. Verified tDCS and MRI safety: Intervention subject should not have any contraindications to either and pass safety screening questions for both (see exclusion section for more information);
10. Capacity to consent, based on responses and ratings to the UCSD Brief Assessment of Capacity to Consent (UBACC) form for this study;

11. Availability of a study partner subject who spends at least several hours per week with the intervention subject, supervises his/her care, and who is willing to accompany the intervention subject to some study visits and participate in the study;
12. Informed consent for study participation obtained by both the intervention subject and his/her study partner subject;
13. Agree to donate 20mL of blood at baseline, after fasting for at least 8 hours (only water and prescribed medicines).

Study partner subject inclusion criteria:

1. Age 18 years or older;
2. English speaking;
3. Has regular contact with MCI intervention subject (at minimum weekly) and be able to answer questions about MCI intervention subjects' current or past well-being or mood.

b) Exclusion Criteria:

Intervention subjects may be excluded from enrollment, or have their enrollment deferred until they are eligible, for the reasons listed below. Final decisions regarding enrollment will be determined by the PI on a case-by-case basis.

1. Presence of any neurological or vascular disorders (e.g. – Multiple Sclerosis [MS], Traumatic Brain Injury [TBI], chronic heart failure [CHF], Parkinson's disease[PD]);
2. Clinical diagnosis of dementia as defined by the most recent version of the DSM;
3. Current enrollment in another study aimed at improving cognitive abilities and/or emotional well-being;
4. MRI contraindications (e.g. – pacemaker, implantable cardioverter defibrillator[ICD], aneurysm clips, severe claustrophobia);
5. tDCS contraindications (e.g. – scalp or skin condition, history of migraines, seizures or epilepsy, and/or strokes, TBI), metallic implants, history of adverse effects to previous tDCS or other brain stimulation techniques).

6. RECRUITMENT METHODS

We will recruit participants using three main recruitment strategies: 1) clinic referrals, 2) established community partners, 3) communities at large. If those strategies fail to reach our recruitment goals, we may initiate additional strategies after IRB approval.

- **Clinic referrals:** participants will be mainly recruited from local clinics, such as the Memory Care Program (MCP) and UR AD-Care, Research and Education Program (AD-CARE) where [name] (Co-I) practices as a geriatric psychiatrist. Other local clinics include the internal medicine and geriatric medicine departments of the University of Rochester Medical Center.
- **Community partners:** We will work with our established community partners e.g. Lifespan, Oasis and YMCA who have helped recruit participants in our preliminary studies. Our community partners will distribute flyers and help arrange talks. **Communities at large:** We will reach out to the broad metropolitan communities by distributing recruitment materials to various venues such as senior centers, churches, libraries, and stores. We will present materials at local

conferences sponsored by organizations such as our local Alzheimer's Association chapter, Area Agency on Aging, and Volunteers of America

- **Recruitment of minority groups:** To emphasize the efforts for minority recruitment, we will reach out to Recruitment Consultation, a core service of Clinical and Translational Science Institute (CTSI) for consultation & recruitment strategy planning.
- **CTSI participant registry:** This study will identify potential subjects for recruiting using the UR CTSI Research Participant Registry, STUDY00001978. Subjects will be sent an email including a flyer for the study, and be asked to respond if interested. If subjects respond with interest, that person will be added to our database and screened normally via phone screening.
- **Emergency Department Research Associate Program (EDRA):** Potential subjects for recruiting will also be identified using the EDRA program. This program utilizes undergraduate research enrollers to screen interested subjects coming through the Strong Memorial Emergency Department. Lab staff will train EDRA staff to administer initial screening materials to gain a list of eligible and interested participants. These participants will then be added to our database and contacted by lab staff for further screening measures. All newly hired EDRAs complete CITI module training on Human Subjects Protection, GCPs, and HIPAA in addition to study specific training.

